### **2.3.5. Changes in male reproductive hormones**

The change in male reproductive hormones (testosterone, follicle-stimulating hormone (FSH), luteinizing hormone (LH) and Inhibin B) for all male participants in all treatment groups from baseline to end of treatment visit (week 17 or week 26 depending on treatment group) and week 39.

### **2.3.6. Changes in lens opacities**

The change (increase or decrease) in lens opacity (cortical, nuclear and posterior subcapsular) from baseline to end of treatment (week 17 or week 26), week 39 and early withdrawal in all participants.

### **2.3.7. Pharmacokinetics (PK) and Pharmacokinetics/Pharmacodynamics (PK/PD)**

This SAP provides descriptive summaries of plasma drug concentrations and PK parameters only. Full details on the full analysis of PK and PK/PD data can be found in the PK/PD modelling SAP.

## **2.4. Other Secondary Efficacy Endpoints**

Other secondary endpoints which will be analysed according to the populations specified:

- Proportion of unfavourable at 24 months (mITT, TB-mITT and PP populations)
- Time to unfavourable status (mITT, TB-mITT and PP populations)
- Time to sputum culture conversion to negative status (mITT population)
- Culture conversion status at 4, 6, 12 and 17 weeks (mITT population)
- Change in weight from baseline (mITT population)
- Change in TB symptoms from baseline (mITT population)
- Change in participant reported health status from baseline (mITT population)
- Adherence (TB-mITT population)
- Baseline predictors of Favourable Status at 12 months (mITT population)

## **2.5. Exploratory Objectives**

### **2.5.1. Predictors of relapse free cure**

Evaluate whether any of the secondary efficacy endpoints as outlined in §2.4 predict relapse free cure at 12 months post randomisation. Potential predictors will include, but are not limited to, baseline variables (see §7.4), culture negative status at weeks 4, 6, 8, 12 and 17 as well as time to culture negativity (as a continuous variable).

### **2.5.2. Subgroup analyses**

Subgroup analyses will be carried out and analysed for the key secondary efficacy endpoint (as described in §2.2 for the TB-mITT population). These subgroups are described in §7.4.

## **3. Definitions and Data Handling Issues**

### **3.1. Positive and Negative Status**

#### **3.1.1. Positive culture**

Positive culture refers to the culture being positive for *Mycobacterium Tuberculosis* (M.tb). The MGIT culture results that are positive with contamination, contaminated, or with no result will be treated as missing.

Two sputum samples per visit are collected at each visit throughout treatment and follow-up. The culture result for a given visit is established using all samples obtained for that visit. A positive culture takes precedence over a negative or contaminated culture at the same visit and a negative culture takes precedence over a contaminated culture at the same visit ([Appendix §13.1](#)).

### **3.1.2. Isolated Positive Cultures**

It is known that occasionally participants produce sputum samples that are “isolated positives,” that is, a positive culture preceded by a series of negative cultures and followed thereafter by at least two negative cultures without an intervening positive result. This phenomenon may be the result of a sealed cavity breaking down or laboratory contamination and does not in itself signify that the participant is relapsing. In the event of a single positive culture result occurring in a participant who has previously been classified as having culture negative status (in the absence of any retreatment), the participant will not be classified as a recurrence unless a second positive culture result is obtained at a separate visit (at least 7 days apart), without an intervening negative culture or unless the participant is lost to follow up or completes the study (and is unable to be brought back) before two negative cultures are obtained. As there is a higher incidence of isolated positives with liquid culture and sometimes even serial “isolated positives” [1], the clinical condition of the participant will also be considered in deciding whether the participant has an unfavourable outcome and re-treatment is indicated.

For example, if a participant after being culture negative has two positive cultures in a row, but is deemed to be doing well clinically, the investigator may choose to leave the participant untreated on clinical grounds. In such a case, so long as two consecutive negative cultures are eventually obtained in the absence of treatment, the participant will not be classified as an unfavourable outcome (defined below).

### **3.1.3. Culture negative status**

Culture negative status is achieved when a participant produces at least two negative culture results at different visits (at least 7 days apart) without an intervening positive culture result for M.tb. The date of the first negative culture (date of collection of culture) of these two is the date at which culture negative status was obtained. Once obtained, culture negative status continues until there are two positive cultures at different visits (at least 7 days apart), without an intervening negative culture, or until there is a single positive culture not followed by two negative cultures. Culture negative status can be achieved at any time during treatment or follow-up but before any re-treatment. Culture negative status can be re-established. A single culture result or inability to produce sputum (see [§3.1.4](#)) at 8 weeks will be sufficient to count that participant as having data for endpoint classification.

Participants with two contaminated or missing samples at a given visit (from month 2 onwards) will be asked to return to produce two more sputum samples.

### **3.1.4. Inability to Produce Sputum**

In general, inability to produce sputum is treated as being equivalent to having a negative culture result if no other sputum sample is produced at that visit. This includes:

- the rare situation where a participant who never achieves culture negative status due to the inability to produce sputum, after TB has been confirmed on the applicable baseline sample, completes follow-up without clinical or microbiological evidence of relapse.
- during the COVID-19 lockdown situation where this data is collected remotely/telephonically.

In SimpliciTB, such participants will be considered to have a favourable outcome and an inability to produce sputum with no other sputum produced at that visit will be treated as a negative culture result.

### **3.2. Bacteriological failure, Relapse or Reinflection**

**Treatment failure** is defined as being declared an unfavourable outcome at or before the end of treatment (either 4 or 6 months) or failing to attain culture negative status and being declared an unfavourable outcome ([§6.2](#)) or the participant is withdrawn at or before the end of treatment for clinical (TB) reasons including being re-treated (or changing from protocol treatment) for TB.

**Relapse or bacteriological relapse** is defined as failing to maintain culture negative status or being declared an unfavourable outcome ([§6.2](#)) after the end of treatment (either 4 or 6 months) in those participants who attained culture negative status by the end of treatment and had culture conversion to positive status with an M.tb strain that is genetically identical to the infecting strain at baseline or after the end of treatment in those participants who attained culture negative status by the end of treatment and were withdrawn for clinical (TB) reasons, including being re-treated (or changing from protocol treatment) for TB. Details are given in [Appendix §13.2](#).

**Reinfection or bacteriological reinfection** is defined as failing to maintain culture negative status or being declared an unfavourable outcome (including being withdrawn for clinical (TB) reasons including being re-treated or changing from protocol treatment for TB) after the end of treatment in those participants who attained culture negative status by the end of treatment and had culture conversion to positive status with a M.tb strain that is genetically different from the infecting strain at baseline. If reinfection cannot be distinguished from relapse, the participant will be assumed to have relapsed. A single positive sample will be sufficient for strain typing to compare to baseline. Full details are in [Appendix §13.2](#).

### **3.3. Adequate Treatment**

The definition of adequate treatment sets a limit for the amount of treatment missed. Participants not taking the adequate amount of treatment by this definition will be excluded from the PP analysis (see [§6.2.3](#)).

Participants allocated to a 4 month regimen, to meet the definition of adequate treatment they must have taken at least 96 doses (80%) of their allocated 119 day (17 weeks) treatment regimen within 175 days of starting therapy (i.e. 17 weeks plus an allowable 56 day halt (including a maximum of 35 consecutive days) as per the protocol).

Participants allocated to a 6 month regimen, to meet the definition of adequate treatment they must have taken at least 146 doses (80%) of their allocated 182 day (26 weeks) treatment regimen within 238 days of starting therapy (i.e. 26 weeks plus an allowable 56 day halt (including a maximum of 35 consecutive days) as per the protocol).

Participants in the control arm are additionally required to have taken at least 80% of their allocated intensive treatment.

### **3.4. Determining Cause of Death**

A list of all **TB-related** and **non-TB-related deaths** will be generated and approved by a review committee **blind to randomised arm** before database lock. Similarly, a list of violent or accidental deaths will be generated (see study Death Adjudication Manual).

### **3.5. Major Protocol Deviations for Analysis**

A major protocol deviation for analysis is defined as a serious protocol deviation which is likely to affect to a significant degree the scientific value of the trial. These participants will be included in the MITT and TB-mITT analyses, but not in the PP analysis (see §6.2). A list of all major protocol deviations for analysis (blinded to treatment arm) will be approved by a review committee prior to database lock.

Note: participants attending a long term outcome visit outside the specified window will be evaluated and considered for potential major protocol violator. Visits within 2 weeks of the window opening will be considered *minor* protocol violators.

### **3.6. Trial Timings**

Study Day 1 is defined as the date on which a participant is administered the first dose of the study medication. Other study days are defined relative to the Study Day 1 with Day 2 being the day after Study Day 1 and Day -1 being the day prior to Study Day 1.

For all safety endpoints, baseline is defined as the last non-missing measurement prior to first dose of study treatment unless otherwise stated.

In all analyses, visit date rather than day or week number will be used to define the timing of events. For participants treated with the 6-month regimens (HRZE/HR for DS-TB participants and 6mBPaMZ for DR-TB participants) this will be taken as a total of 26 weeks, i.e. 182 dosing days. For DS-TB participants randomised to 4 months of BPaMZ a total of 17 weeks (119 dosing days) is taken. As per the protocol, assessments should be collected as follows:

- Within  $\pm 3$  days of scheduled visit from day 1 to week 8
- Within  $\pm 5$  days of scheduled visit from week 12 to week 26
- Within  $\pm 14$  days of scheduled visit during the follow-up phase at or after month 6 to month 24.

Unscheduled visits and visits outside of these windows will be slotted into windows as appropriate. Visits falling outside of the defined protocol visit windows will be put into separate visits so that all data, both collected at scheduled and unscheduled time points, are used.

The **treatment period** is defined as either 17 or 26 weeks from start of therapy depending on allocated treatment regimen.

The **follow-up period** is defined as the period after the end of treatment to the end of follow-up.

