### **2.3.3. Clinical safety laboratory measurements**

The incidence of newly notable (an abnormality observed post baseline that meets the notable criteria) grade 3 or 4 severity for laboratory parameters according to DMID grading. Participants are considered to have notable laboratory abnormalities if his/her response falls within the specified definitions (see Table 3 in §8.3.1) at least once during the treatment period.

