### **3.7. General Statistical Considerations for Safety Analysis**

If there are multiple assessments in a visit, the highest grade non-missing value within a visit will be used in the summaries, however all will be shown in the listings. If numeric data is beyond range of lab detectability and result is showed as “<XX” or “>XX” then the numeric XX value will be used for summary statistics.

There will be no specific strategy to deal with missing data i.e. it will not be imputed. A complete case analysis will be performed. For example when modelling the data based on a specific outcome only participants with complete data will be included.

Baseline is defined as last available measurement prior to dosing and post baseline abnormalities are included in the summary if the subject did not meet the abnormality criteria at baseline or toxicity grade at post baseline is higher than that on baseline.

All statistical analyses tables, listings and figures will be produced using STATA Version 16.0 or higher.

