### **3.8. Newly notable abnormalities**

A newly notable laboratory abnormality is defined as an abnormality observed post baseline that meets the notable criteria in [Table 3](#) and that did not exist at baseline. Participants can still meet the criteria for newly notable laboratory if the baseline value is missing.

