## **8.3. Clinical Evaluation**

### **8.3.1. Clinical Laboratory Evaluation**

A list of laboratory tests (haematology, clinical chemistry, and urinalysis) to be included in the analysis is presented in [§7.3 of the protocol](#). Laboratory assessments done by a central laboratory will be summarised in tables. All summaries will be based on the units provided by the central laboratory, no conversion will be done. The laboratory evaluations will be summarised for baseline, post-baseline, and change from baseline at week 8, end of treatment (week 17 or week 26), 52 week and 104 week FU.

Laboratory values outside normal ranges will be identified, and the number and percentage of participants with at least one post-baseline abnormality will be summarised in shift tables comparing the baseline results to each post-baseline timepoint for those participants with results at both timepoints.

The table below displays the general variables and thresholds of interest. Participants are considered to have notable laboratory abnormalities if his/her response falls within the specified definitions at least once during the treatment period.

Table 3:Notable Criteria for Laboratory Data

Lab Test Type	Laboratory Variable	SI Units
Liver	AST	>3 x ULN and ≤ 5 x ULN >5 x ULN and ≤ 8 x ULN >8 x ULN
	ALT	>3 x ULN and ≤ 5 x ULN >5 x ULN and ≤ 8 x ULN >8 x ULN
	Total Bilirubin	>2 x ULN
	Alkaline Phosphatase (ALP)	>2 x ULN
Chemistry Labs	Other: ALT or AST > 3 x ULN and total bilirubin > 2 x ULN ALT or AST > 3 x ULN and total bilirubin > 2 x ULN and ALP < 2 x ULN (potential Hy's law case)	
	Lipase	>2xULN to ≤5XULN >5xULN

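### Table 3 laboratory abnormalities, including the potential Hy's law count, are limited to a fixed 17- or 26-week window that can close while participants are still on drug

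*SAP*

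**What the plan says.** Section 2.3.3 treats a participant as having a notable laboratory abnormality if the result "falls within the specified definitions (see Table 3 in §8.3.1) at least once during the treatment period". Section 8.3.1 repeats the rule directly above Table 3: a participant counts if "his/her response falls within the specified definitions at least once during the treatment period". The last liver row of Table 3 combines raised ALT or AST with "total bilirubin > 2 x ULN and ALP < 2 x ULN" and is labelled as a potential Hy's law case.

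Section 3.6 defines the treatment period. It "is defined as either 17 or 26 weeks from start of therapy depending on allocated treatment regimen". The same section adds that "visit date rather than day or week number will be used to define the timing of events", and it allows visits from week 12 to week 26 to be up to 5 days early or late.

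Three other places describe abnormalities without an end date. Section 2.3.3 glosses newly notable as "an abnormality observed post baseline that meets the notable criteria". Section 3.8 begins "A newly notable laboratory abnormality is defined as an abnormality observed post baseline that meets the notable criteria in" and points to Table 3. Section 3.7 says "post baseline abnormalities are included in the summary if the subject did not meet the abnormality criteria at baseline", or if the grade has risen since baseline.

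Three further rules bear on the point:
- Section 3.3 accepts treatment as adequate when it is spread over as many as 175 days (4-month regimen) or 238 days (6-month regimens), which allows for 56 days of halts.
- Section 2.3 follows treatment-emergent adverse events to 14 days after the last study drug.
- Section 5 analyses the Safety population by treatment received.

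**The concern.** The laboratory window is tied to the calendar and to the allocated regimen. Drug exposure, as the SAP itself accepts it, is not. A participant who halts and resumes can still be taking study drug after the treatment period has formally ended. An ALT and bilirubin rise in those weeks would be on-drug liver toxicity, yet the wording of Sections 2.3.3 and 8.3.1 leaves it out of Table 3.

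The SAP expects interruptions: Section 8.2.5 tabulates interruptions due to adverse events and Section 11.1.4 tabulates dose pauses. At stake is the completeness of the one table that counts the combined transaminase and bilirubin criterion. Two programmers could also produce different counts, depending on whether they apply the definition in Section 3.6 literally.

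**Working it through.** **Inputs.** Regimen lengths of 17 and 26 weeks and the 5-day visit allowance come from Section 3.6. The 56-day halt allowance and the 175- and 238-day limits come from Section 3.3. The 14-day extension for adverse events comes from Section 2.3.

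**Reproducing the SAP's own figures.** 17 x 7 = 119 and 119 + 56 = 175. 26 x 7 = 182 and 182 + 56 = 238. Both agree with Section 3.3.

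**Where each rule ends, in days from start of therapy.**

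| Rule | 4-month | 6-month |
|---|---|---|
| Treatment period, literal reading | 119 | 182 |
| End-of-treatment visit 5 days late | 119 + 5 = 124 | 182 + 5 = 187 |
| Last dose + 14 days, no halt | 119 + 14 = 133 | 182 + 14 = 196 |
| Latest accepted dosing | 175 | 238 |
| Last dose + 14 days, full halt | 175 + 14 = 189 | 238 + 14 = 252 |

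**Gaps.** Accepted dosing can outlast the literal window by 175 - 119 = 56 days, or 238 - 182 = 56 days. The adverse-event window can outlast it by 14 days with no halt and by 189 - 119 = 70 days (252 - 182 = 70) with a full halt.

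**Upper bound for one participant.** Assume all 56 halt days fall before the nominal end and every dose is made up.
- 4-month regimen: 119 - 56 = 63 dosing days fall inside the window and 56 outside, so 56/119 = 47% are missed.
- 6-month regimens: 182 - 56 = 126 fall inside and 56 outside, so 56/182 = 31% are missed.

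Section 3.3 caps any single halt at 35 consecutive days, so this case needs at least two halts.

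**Does the newly notable wording settle it?** No. Sections 2.3.3 and 3.8 say when such an abnormality starts to count and refer to the Table 3 criteria. They neither extend nor replace the limit on notable abnormalities.

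**Is the combination counted elsewhere?** Section 8.2.8.3 counts ALT or AST at or above 3 x ULN, or a hepatic serious event, and does not use bilirubin. The shift tables in Section 8.3.1 compare results with normal ranges. The tables in Section 8.2.8 and the hepatic grouping in Note to File 2 count reported adverse events. Note to File 3 plots ALT, AST, ALP and bilirubin for participants with grade 3 or higher ALT or AST, but a plot is not a count.

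**The case against.** A reader might infer that the SAP sets two rival windows for Table 3, one ending with the treatment period and one open-ended. The text does not establish that. Newly notable can be read as nested within notable: post baseline gives the start, treatment period gives the end, and Section 3.7 says how a result is judged against baseline. The absence of an end date in those sentences is silence. This answers the claim of contradiction, but the nested reading keeps the literal limit and therefore the omission.

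Section 3.6 also allows a softer reading. It equates the regimens with 119 and 182 dosing days and defines follow-up as beginning when treatment ends, which suggests a period lasting as long as dosing does. That reading is fair, but the definition itself counts weeks from the start of therapy and does not mention halts.

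The late-visit route is weaker. By date, a sample on day 120 to 124 or 183 to 187 falls outside the period. However, Section 3.6 accepts it as the scheduled week 17 or 26 visit and aims to use all data, so this is a secondary route only.

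It is also true that Section 3.3 serves the per-protocol exclusion and is not a safety window, that it requires only 80% of doses, and that the protocol, not shown here, may determine whether blood is drawn in the extra weeks. The 47% and 31% are therefore bounds, not expectations. Finally, safety is purely descriptive, so no test or decision depends on the count.

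**Conclusion.** The point stands as a gap in one count. On the literal wording, Table 3 can miss abnormalities arising on drug for up to 56 days after day 119 or 182. For the combined ALT/AST and bilirubin criterion, no other planned count recovers them. The limit is also out of step with the adverse-event window, which follows actual dosing, and with the as-treated Safety population, since the period follows the allocated regimen.

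The conclusion assumes that the definition in Section 3.6 is applied as written and that laboratory results exist in the weeks concerned. The number of participants affected cannot be derived, because the SAP gives no frequency of halts or late visits.

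A reader might infer that potential Hy's law cases would disappear from the report. The SAP does not support that: listings, the hepatotoxicity proportion, the hepatic adverse-event tables and the liver plots would show some of them. No efficacy result is touched. The change is worth making because it is cheap and the count is an important liver-safety summary.

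**What to change.** In Sections 2.3.3 and 8.3.1 only, replace the reference to the treatment period with: *from first dose to 14 days after the actual last dose, or to the nominal end of treatment for the regimen received if later*. In Section 3.8, state that newly notable abnormalities use the same window. Leave Sections 3.6 and 3.7 and every other use of treatment period as they are.

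With no halt, the window ends at day 133 or 196 and so includes an end-of-treatment visit 5 days late (day 124 or 187). After a full halt it runs to day 189 or 252. Participants who stop early are still counted to the nominal end. For them the window can be longer than the adverse-event window, which is a deliberate choice so that the change shortens nobody's window for the regimen received.

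The cost is a wording change in three sections and the matching programming, with no new data or tables. The downside is that window length varies between participants, as the adverse-event window already does. The change concerns the analysis window alone and alters no dosing or halt rule.
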